## 1. INTRODUCTION/SIGNIFICANCE

**The purpose of this study is to identify the impact of a structured exercise program on sympathetic nervous system activity (SNA) and vascular function in pregnancy.** Sympathetic hyperactivity and associated vascular dysfunction are closely tied to hypertension and cardiovascular disease(17) and may be an important mechanistic link between pregnancy complications and the development of future cardiovascular disease in both the mother and child(16). During normal pregnancy, sympathetic activity is elevated yet the transduction of this signal to a blood flow or vascular response is typically blunted (26). In pregnancies where women develop high blood pressure, sympathetic activity is even higher (11; 12; 21) and the transduction of this signal does not appear blunted (20; 29). In non-pregnant populations, exercise is considered an effective, low cost means to improve cardiovascular disease risk (1). Exercise training has been shown to reduce sympathetic activity in other clinical populations, improving cardiovascular function (2). Exercise is recommended to all healthy pregnant women, yet, the impact of exercise during pregnancy on vascular (peripheral and cerebral) and sympathetic function is virtually unknown. Understanding the role of exercise in modulating SNA and vascular function during pregnancy is important for the development of lifestyle recommendations and interventions to promote cardiovascular health in pregnant women. Therefore we goal of this study is to examine the potential benefits of prenatal exercise on neurovascular function.

## 2 STUDY OBJECTIVES

### 2.1. Specific Aims

- 1) *Determine the role of exercise in regulating sympathetic activity during pregnancy.*
- 2) *Determine the impact of exercise on vascular reactivity and function during pregnancy.*

### 2.2. Hypotheses

- 1) *We hypothesize that exercise training will blunt the increase in SNA which occurs with pregnancy.*
- 2) *We hypothesize that vascular reactivity to sympathetic stressors will be reduced in women who are taking part in a structured exercise program compared to those that have not.*

## 3 PATIENTS AND METHODS

### 3.1 Study Design

#### *General Design*

BASELINE (16-20 weeks), POST-INTERVENTION (34-36 weeks), AND POSTPARTUM (2 months): At each time-point during pregnancy, participants will report to the laboratory on two occasions. Women will report to the laboratory once in the postpartum.

**Visit 1)** Participants will complete a peak exercise test on the treadmill or bike to volitional fatigue. Instrumentation will include breathing through a mouthpiece attached to a metabolic cart (measures how and what the participant is breathing), heart rate, blood pressure and transcranial doppler ultrasound (TCD) to measure blood flow in the brain (middle cerebral artery). Resting diameter and flow of the internal carotid artery (ICA) will be assessed at rest. Lung capacity will be assessed at rest using spirometry. Participants will then warm up for 5 minutes at 3.4mph and 0% grade. After the warm up, the incline will increase in 1% increments until volitional fatigue. The test will be followed by a 5 minute cool down. Participants will hold the hand-rails through-out the peak test (5; 7). Exercise on the bike will follow a similar protocol of 5 minutes of rest, 5 minutes of warm-up at 0.5kpa. Exercise intensity will increase by 0.5kpa until volitional fatigue, followed by a 5 minutes of cool down and 5 minutes of rest.

**Visit 2)** Participants will arrive after refraining from exercise, caffeine, alcohol or food for 12 h (overnight fast) and blood samples will be collected. Following centrifugation, aliquots will be frozen at -80°C until analysis. A finger poke will be used to measure glucose via glucometer and blood gases and metabolites (blood gas analyzer). Following the blood draw, anthropometrics will be recorded and a standardized breakfast will be provided. Participants will then undergo an assessment of reflex neurovascular control. Participants will rest in a dentist chair 30° above supine for the duration of testing to minimize discomfort of the pregnant women.

After instrumentation (described below) and an initial period of 20 min of rest, participants will undergo baseline testing which consists of arterial stiffness (pulse-wave velocity and ultrasound) and carotid distensibility. Next, participants will undergo 3 separate conditions separated by 20 minutes of quiet rest: **1)** 3 min with their hand in an ice bath (cold pressor test); **2)** Flow mediated dilation (~15 minutes) and **3)** an end expiratory breath hold (~15s). Following the cold pressor test a heating pad will be used to warm the hand to baseline temperature.

**Postpartum Visit)** Participants will arrive after refraining from exercise, caffeine, alcohol or food for 12 h (overnight fast) and blood samples will be collected. Following the blood draw, anthropometrics will be recorded and a standardized breakfast will be provided. Participants will then undergo an assessment of blood vessel health. After instrumentation (described below, but without microneurography), participants will undergo testing which consists of arterial stiffness (pulse-wave velocity and ultrasound) and carotid distensibility. Following this, participants will undergo an assessment of flow mediated dilation (described above).

#### *Primary Outcome Variables: Basal SNA*

SNA bursts will be visually identified as exhibiting pulse synchrony, having an amplitude two times the previous inter-burst period, and characteristic rising and falling slopes. SNA will quantified as burst frequency (bursts/min), burst occurrence (bursts/100 heartbeats), and burst amplitude (% of baseline).

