### 3.2 Subject Selection and Withdrawal

One hundred pregnant women (>18yrs, with singleton pregnancies) will be recruited between 16-20 weeks gestation through physician and midwife referrals, newspaper advertisements and recruitment posters. Women diagnosed with multiple pregnancies will be excluded. Eligible women will be randomized to take part in an exercise intervention (n=50) or no intervention (n=50). The intervention will consist of aerobic exercise equivalent to 50-70% of heart rate reserve, 3-4 times per week until the end of the study (34-36 weeks). For initial baseline testing (16-20 weeks) and at the end of the intervention (34-36 weeks), participants will visit the laboratory twice. Following initial baseline testing, women will be randomly assigned to an exercise intervention or no intervention. Women will receive an opaque sequentially numbered envelop with their allocation. Allocation will be determined using a randomly generated allocation sequence by an individual not associated with the research study who will place and seal the allocation in the envelope.

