#### Sympathetic Nerve Activity

SNA directed at the vasculature within skeletal muscle will be assessed by microneurography(13). A sterile tungsten microelectrode (35 mm long; 200  $\mu$ m in diameter; tapered to a 1- to 5- $\mu$ m uninsulated tip) will be inserted transcutaneously into the fibular nerve posterior to the fibular head with a reference electrode positioned subcutaneously 1-3 cm away. SNA will be obtained by manually manipulating the microelectrode until a characteristic pulse-synchronous burst pattern(8). The raw SNA signal will be amplified, band-pass filtered (700-2,000 Hz), rectified and integrated to obtain a mean voltage neurogram (0.1-s time constant). SNA data will be sampled at 10,000 Hz and stored for off-line analysis (Powerlab Software, ADInstruments).

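### The plan does not mask the person who identifies SNA bursts by eye to arm; reading the stored recordings under code would largely prevent arm-related bias at that stage

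*Combined protocol and SAP*

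**What the plan says.** Under Primary Outcome Variables: Basal SNA, "SNA bursts will be visually identified as exhibiting pulse synchrony". A burst must also reach twice the amplitude of the preceding burst-free interval and have the typical shape of rise and fall. The outcome is then expressed as burst frequency, burst occurrence per 100 heartbeats, and "burst amplitude (% of baseline").

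Section 2.2 sets a directional hypothesis: "We hypothesize that exercise training will blunt the increase in SNA which occurs with pregnancy". Section 3.2 gives the comparison: "Eligible women will be randomized to take part in an exercise intervention (n=50) or no intervention (n=50"). Randomisation follows baseline testing and uses opaque, sealed, sequentially numbered envelopes: "Allocation will be determined using a randomly generated allocation sequence by an individual not associated with the research study".

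Section 3.3, Sympathetic Nerve Activity, separates acquisition from reading. Acquisition is live and depends on the operator: "SNA will be obtained by manually manipulating the microelectrode". Reading can be done later: "SNA data will be sampled at 10,000 Hz and stored for off-line analysis". The postpartum visit carries no SNA measurement ("After instrumentation (described below, but without microneurography")), so only the baseline and 34-36 week visits contribute to the primary outcome.

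Section 3.4 analyses basal SNA with a two-way (group by time) mixed ANOVA. Section 4.1 gives each participant a study code after consent. No section of the supplied text states who reads the neurograms or that the reader, outcome assessor or analyst is masked to arm.

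**The concern.** An exercise programme cannot be hidden from the women taking part, and testing staff may well know who is training. Masking the reader is therefore the main protection available for a primary outcome that rests partly on judgement. Pulse synchrony and the amplitude rule can be checked against the trace. The shape criterion has no threshold, so it leaves room for expectation to influence which borderline deflections are counted.

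If that influence differs between arms at 34-36 weeks, it goes straight into the group comparison of the primary outcome. It would also reach the vascular transduction outcome in Secondary Outcome Variables, item A, which is calculated from beats that carry a burst and stratified by burst amplitude. The plasma markers in item C do not depend on burst reading and give a partial cross-check, but they are secondary.

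**Working it through.** **Step 1: does any provision mask the reader?**

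| Provision | Where | What it does | Masks the reader? |
|---|---|---|---|
| Opaque sealed envelopes, sequence made by an outsider | 3.2 | Conceals allocation until assignment | No; every 34-36 week recording is made after assignment |
| Participant code, locked master list | 4.1 | Protects identity | Not stated to hide arm or visit from the reader |
| Burst criteria | 3.1, Basal SNA | Define a burst | No |
| Storage for off-line analysis | 3.3 | Makes later coded reading possible | Not by itself |

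None of the four amounts to masking, so the omission is established from the text.

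**Step 2: how large could the effect be?** The plan gives no figure for reading error, so there is none to reproduce on this point. The related sample-size figure of 22 (section 3.4) serves below as the lower analysed number per arm. The two-sided normal approximation for a difference of 9 and SD 11 gives 2 × (1.960 + 0.842)² × 11² / 9² = 23.5, rounded up to 24, which is close to 22 if 22 is a per-arm number.

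Inputs:
- SD 11 bursts/min (section 3.4).
- n per arm from 22 (section 3.4) to 32, since 50 × 0.80 × 0.80 = 32 (section 3.4: 80% signal success, 80% retention).
- Two SNA visits (section 3.1).
- Two-sided alpha 0.05 and no true effect of exercise. The plan gives 0.05 without stating sidedness.
- Assumed, not in the documents: a differential reading shift k of 1 or 2 bursts/min at 34-36 weeks only, and a between-visit correlation r of 0.3 to 0.7.

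The Statistical Methods text does not name the decisive ANOVA term, so both are shown:
- Interaction: the difference is k, and the SD of change is 11 × √(2(1 − r)), i.e. 13.02, 11.00 and 8.52 for r = 0.3, 0.5 and 0.7.
- Group main effect: the difference is k/2, and the SD of the two-visit mean is 11 × √((1 + r)/2), i.e. 8.87, 9.53 and 10.14.

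The noncentrality is difference / (SD × √(2/n)) with 2n − 2 degrees of freedom. The false-positive rate is the two-sided rejection probability of the noncentral t. For example, with k = 2, r = 0.5 and n = 32, the interaction has noncentrality 2 / (11 × √(2/32)) = 0.727 and a rejection rate of 11.1%.

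| k | r | Interaction, n = 22 / 32 | Main effect, n = 22 / 32 |
|---|---|---|---|
| 1 | 0.3 | 5.7% / 6.1% | 5.4% / 5.6% |
| 1 | 0.5 | 6.0% / 6.5% | 5.3% / 5.5% |
| 1 | 0.7 | 6.7% / 7.5% | 5.3% / 5.4% |
| 2 | 0.3 | 7.9% / 9.3% | 6.5% / 7.3% |
| 2 | 0.5 | 9.1% / 11.1% | 6.3% / 7.0% |
| 2 | 0.7 | 11.9% / 15.2% | 6.2% / 6.7% |

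A simulation of 60,000 runs at k = 2 agrees. For n = 22 and r = 0.3 it gives 7.8% (interaction) and 6.5% (main effect); for n = 32 and r = 0.7 it gives 15.0% and 6.7%.

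**Step 3: which masking matters most?** A reading shift by visit that is equal in both arms adds the same amount to each arm's change and cancels in the interaction. Hiding the arm therefore does most of the work. Hiding participant and visit mainly helps to keep the arm hidden.

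**The case against.** The strongest reply is that silence is not evidence of unmasked reading. A short protocol may leave out a laboratory practice that is in fact followed, and nothing in the documents shows that a reader will know the arm. That is correct. The point is only that the plan does not provide for masking; if coded reading is already the practice, one added passage records it.

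Second, participant codes exist and nothing suggests that they carry the arm, so a reader with no participant contact might in effect be masked. This may be so, and the codes supply part of the fix. But the plan does not separate the reader from the staff who test or train the women, so it offers no guarantee.

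Third, discretion is bounded: if a candidate must first pass the synchrony and amplitude rules, the shape judgement can only reject. This stands as a limit on the likely size of any shift, not as a reason to leave the reader unmasked.

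Fourth, the error rates rest on assumed values of k and r, and the 15% end needs k = 2, r = 0.7 and n = 32 together, on the interaction. At k = 0.5 the interaction rate is only about 5.2-5.6%. This also stands. The figures illustrate; the case rests on the qualitative argument.

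Stored files could be re-scored under code later, but the plan does not provide for it, and a check made after results are known protects less.

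**Conclusion.** The concern holds. A primary outcome read partly by judgement, in a trial whose participants cannot be masked and whose hypothesis has a direction, has no stated masking of the reader. The gap in the text is certain; whether bias would follow, and how much, is unknown. Under the stated assumptions a differential shift of 2 bursts/min, under a quarter of the planned difference of 9, would matter moderately on the interaction and little on the group main effect, while 1 burst/min would matter little on either. The change should be made because it is cheap and protects the primary comparison, not because serious bias has been shown.

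**What to change.** Add to the primary outcome definition in section 3.1:

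> Each stored baseline and 34-36 week neurogram is given a random recording-level code that hides arm, participant and visit. The key is held by someone other than the reader. Burst identification, and any off-line decision on signal acceptability, are completed and locked under that code before unblinding. Any normalisation of burst amplitude that needs the baseline visit is calculated after locking.

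Signal acceptability is included because section 3.4 expects one recording in five to fail, and rejecting recordings with the arm known would be another route to bias. The last sentence is needed because the plan expresses amplitude relative to baseline without saying whether that means the baseline visit.

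The cost is a small recoding task and a named key-holder. No participant procedure is added and the sample size does not change. The benefit is confined to the reading stage: heart rate on the trace may hint at training status or visit, and live electrode placement remains unmasked.

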#### *Secondary Outcome Variables:*

**A) Sympathetic reactivity and vascular transduction.** Basal vascular transduction and changes during the cold pressor test will be compared between groups to identify differences in vascular reactivity associated with exercise training. Femoral artery conductance will be calculated as blood flow divided by mean arterial pressure. Vascular transduction of sympathetic activity will be calculated for each heart beat that has a burst of SNA, as well as for the subsequent 15 beats. The time course of conductance following bursts of SNA (percent change) will be averaged and further stratified by burst amplitudes (9). Cerebrovascular reactivity to exercise (a major sympathetic stressor) will also be compared between groups to assess the impact of exercise training and on brain blood vessels reactivity.

**B) Arterial Stiffness (Pulse-wave velocity).** Basal arterial stiffness and changes during cold pressor test will be compared between groups to identify differences in vascular structure and function associated with normal and hypertensive pregnancies (6; 24).

**C) Sympathetic neurotransmitters.** Biochemical analyses will be conducted to determine plasma concentrations of epinephrine, norepinephrine, and neuropeptide-Y (ELISA) as secondary markers of sympathetic activation (24).

**D) Sex hormones.** Progesterone, estrogen, testosterone and their ratio influence basal SNA and vascular function (3; 15). As such, plasma sex hormones and the ratio between progesterone and estrogen will be determined (ELISA).

**E) Blood volume.** Vasopressin, aldosterone, plasma renin activity, plasma osmolality, Na, Cl, K.

**F) Respiratory measures.** Ventilation (l/min), and both inspired and expired Oxygen and Carbon dioxide will be measured during the initial baseline period. Lung capacity will also be measured prior to the exercise test (day 1).

#### *Tertiary Outcome variables*

**A) Insulin and glucose measurement.** Insulin has been shown to increase SNA in healthy and diabetic individuals (14). Vascular (both peripheral and cerebral) function is altered by these hormones. As insulin resistance increases during pregnancy, fasted measures of glucose and insulin (Day1) will be analyzed to

determine their relationship to the primary outcome measures. Insulin sensitivity will be determined using the HOMA equation (18).

**B) Arterial Stiffness and Endothelial-dependant Dilation.** Arterial stiffness and endothelial function will be assessed to determine the influence of exercise on other measures of vascular function.

### 3.2 Subject Selection and Withdrawal

One hundred pregnant women (>18yrs, with singleton pregnancies) will be recruited between 16-20 weeks gestation through physician and midwife referrals, newspaper advertisements and recruitment posters. Women diagnosed with multiple pregnancies will be excluded. Eligible women will be randomized to take part in an exercise intervention (n=50) or no intervention (n=50). The intervention will consist of aerobic exercise equivalent to 50-70% of heart rate reserve, 3-4 times per week until the end of the study (34-36 weeks). For initial baseline testing (16-20 weeks) and at the end of the intervention (34-36 weeks), participants will visit the laboratory twice. Following initial baseline testing, women will be randomly assigned to an exercise intervention or no intervention. Women will receive an opaque sequentially numbered envelop with their allocation. Allocation will be determined using a randomly generated allocation sequence by an individual not associated with the research study who will place and seal the allocation in the envelope.

#### 3.2.1 Inclusion Criteria

Healthy, premenopausal, women, 18 years or older. Clearance to exercise in writing or using the PARmed-X for Pregnancy.

#### 3.2.2 Exclusion Criteria

Women diagnosed with multiple pregnancies (twins etc). Contraindications to exercise/lack of physician clearance.

### 3.3 Study Procedures

*The principle and co-investigators have expertise in and have previous experience with and have published manuscripts utilizing all of the proposed techniques.*

*Cold Pressor Test:* The cold pressor test involves submersing the hand up to the wrist in an ice-bath (~0-4° C). The cold stimulus is simple to apply, familiar to most individuals and elicits a strong nociceptive (pain) reflex. This causes a large increase in SNA which causes an acute, yet robust increase in blood pressure(27). The participant can self-terminate the test at any point by removing their hand from the ice-bath. A heating pad will be used to re-warm the hand upon termination of the test.

*Expiratory Breath-hold:* Participants with breath normally (e.g. no preceding hyperventilation), following a normal breath out they will hold their breath for as long as possible (usually < 30s). This will cause a near maximal activation of the sympathetic nervous system (22; 23).

*Flow mediate dilation:* Flow mediated dilation is a standard, non-invasive measure of endothelial function. Brachial artery diameters will be assessed at rest for 1-2 minutes (ultrasonography). A standard blood pressure cuff will then be inflated to supra-systolic pressure for 5 min. The return to flow following deflation of the cuff results in an increase stimulus in the artery leading to dilation. This dilation will be measured over 5 min following cuff deflation (25).

#### Sympathetic Nerve Activity

SNA directed at the vasculature within skeletal muscle will be assessed by microneurography(13). A sterile tungsten microelectrode (35 mm long; 200  $\mu$ m in diameter; tapered to a 1- to 5- $\mu$ m uninsulated tip) will be inserted transcutaneously into the fibular nerve posterior to the fibular head with a reference electrode positioned subcutaneously 1-3 cm away. SNA will be obtained by manually manipulating the microelectrode until a characteristic pulse-synchronous burst pattern(8). The raw SNA signal will be amplified, band-pass filtered (700-2,000 Hz), rectified and integrated to obtain a mean voltage neurogram (0.1-s time constant). SNA data will be sampled at 10,000 Hz and stored for off-line analysis (Powerlab Software, ADInstruments).

#### Cardiovascular Measures

The electrocardiogram (lead II) and blood pressure waveform (photoplethysmography; Finapres Medical Systems) will be recorded continuously to derive heart rate, mean, systolic, and diastolic blood pressures on a beat-by-beat basis. Blood pressure will validated by automatic sphygmomanometer measurements at the brachial artery. Cardiac output will be calculated on a beat-by-beat basis using the Model Flow Method(28).

Continuous common femoral artery blood flow velocity will be collected from the opposite leg as SNA (Doppler ultrasonography; GE Vivid-7, 14 MHz linear probe). B-mode images of the carotid and femoral artery will be recorded for measurement of diastolic and systolic diameters at baseline and the end of the hyperoxia and/or cold pressor tests. Blood flow velocity and diameters will be used to calculate volumetric flow. Uterine artery blood flow, resistance and pulsatility index will be assessed at rest.

#### *Arterial stiffness*

Pulse-wave velocity will be measured as a clinical index of arterial stiffness(19). Continuous carotid artery blood pressure waveforms will be collected 1–2 cm proximal to the carotid bifurcation using hand-held tonometry (Millar Instruments). Simultaneously, continuous common femoral artery blood pressure waveforms will be collected from the right leg for assessment of carotid-femoral pulse wave velocity which is the gold standard measure of central arterial stiffness (Millar Instruments)(19). Peripheral stiffness will be measured from carotid-finger pulse-wave velocity (tonometer to finger photoplethysmography).

